5.5.4.1 Anticipated Adverse Events

Anticipated Adverse Events are complications that are known to be associated with aneurysm and non-aneurysm lesions of the aortic arch and DTA patients undergoing treatment with the TBE Device.

5.5.4.1.1 Adverse Event Relationship

GORE CONFIDENTIAL INFORMATION

Each reported AE will be assessed by the Investigator for its primary suspected relationship to the device, surgical revascularization procedure, and/or endovascular procedure. It is permissible to assign multiple relationships for each reported AE.

Related to Device

The functioning or characteristics of the implanted device(s) caused or contributed to the Adverse Event. This is applicable to all components of the TBE Device (Aortic Component, Aortic Extender, Side Branch Component) as well as the CTAG Device.

Related to Surgical Revascularization Procedure

The surgical revascularization procedure (Zone 0/1 Subjects) (and not the device(s)) caused or significantly contributed to the Adverse Event.

Related to Endovascular Procedure

The endovascular procedure (and not the device(s)) caused or significantly contributed to the Adverse Event.

Related to Device and Endovascular Procedure

The endovascular procedure as well as the device(s) caused or significantly contributed to the Adverse Event.

Unrelated to Devices and Procedures

An Adverse Event which cannot be attributed to the device(s) or procedure(s).

Unknown relationship

The relationship of the Adverse Event to the device or procedure cannot be determined.

5.5.4.1.2 Adverse Event Classification

Each AE will be assessed by the Investigator to determine if it is serious or non-serious².

Serious Adverse Event

A Serious Adverse Event is an Adverse Event that

- led to death •
- led to serious deterioration in the health of the Subject • that either resulted in
 - a life threatening illness or injury, or
 - a permanent impairment of a body structure or body function, or

GORE CONFIDENTIAL INFORMATION

- inpatient or prolonged hospitalization, or
- o medical or surgical intervention to prevent life threatening illness or injury or permanent impairment to a body structure or a body function
- led to fetal distress, fetal death or a congenital ٠ abnormality or birth defect.

Non-Serious Adverse Event

Any event that does not meet the definition of serious will be classified as non-serious.

5.5.4.1.3 Adverse Event Reporting and Coding

AEs will be reported on the appropriate CRF and documented in the Subject's permanent medical record. The Investigator at each Site is ultimately responsible for reporting AEs to the Sponsor.

The following information on each reported Adverse Event will be collected:

- Adverse Event Name •
- Adverse Event Onset Date •
- Relationship
- Classification (Serious or Non-Serious) •
- Treatment
- Outcome
- **Resolution Date**

Adverse Events will be coded using the Medical Dictionary for Regulatory Activities (MedDRA).

Adverse Event submission guidelines:

- Adverse Event reporting begins once the patient is enrolled in the study. All Adverse Events should be reported from enrollment through study completion / discontinuation.
- Provide a diagnosis if possible. If unable to provide a • diagnosis, report the symptoms as separate events. Adverse Events should be reported using the full name without abbreviations or narratives.
- Adverse Events with an outcome status of "Ongoing" • should be assessed at each follow-up evaluation to determine if the event has resolved. Adverse Events ongoing at study completion / discontinuation should be left as "Ongoing" on the AE case report form.

GORE CONFIDENTIAL INFORMATION

5.5.4.1.4 Subject Death

Death is not an AE itself, but instead an outcome of an AE. Therefore, the cause of death, if known, should be the reported AE.

Any ongoing or unresolved AEs at the time of death will be indicated as ongoing/continuing on the CRF. Attempts should be made by the investigative Site to obtain death certificates, autopsy reports and device explants when at all possible.

5.5.4.2 Unanticipated Adverse Device Effects (UADEs)

An unanticipated adverse device effect (UADE) is defined as any serious adverse effect on health or safety or any life-threatening problem or death caused by, or associated with, a device, if that effect, problem or death was not previously identified in nature, severity or degree of incidence in the investigational plan or protocol.

5.5.5 Core Laboratory Analysis

An independent Core Laboratory (Core Lab) will provide review of imaging data collected during the study at pre-treatment and follow-up.

Summaries of qualitative (yes/no, false lumen status categories) Core Lab imaging findings will be analyzed for each applicable analysis window. If there is more than one imaging finding for a Subject within a specific analysis window, the worst case finding will be used for summary in the window. The denominator for each window will be the number of Subjects with a non-missing Core Lab finding (such as either yes or no) in the given window.

Summaries of quantitative measurements will be calculated using the measurement obtained

Core Lab data will not be reconciled with Site-reported data.

5.5.6 Mortality

For additional analysis of all-cause mortality (in addition to Success Outcomes), Kaplan Meier methodology will be used. Subjects without death reported before the end of the time period of

GORE CONFIDENTIAL INFORMATION

interest will be censored at the Subject's last reported contact date or the end of the time period of interest, whichever date is earlier.

For additional analysis of lesion-related mortality (in addition to Primary Endpoint and Success Outcomes), Kaplan Meier methodology will be used. Subjects without a lesion-related death reported before the end of the time period of interest will be censored at the Subject's last reported contact date or the end of the time period of interest, whichever date is earlier.

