Expected Time to Complete Enrollment	
 • Zone 2 - Aortic Aneurysm Subject accrual: 18-24 months • Zone 0/1 - Aortic Aneurysm Subject accrual: 48-60 months • Follow-up – Five years from treatment date Total study duration –Ten years
Schedule of Events Zone 2 Cohorts	
Screening Evaluation: (Within 30 days prior to enrollment unless otherwise noted)
 
 • Physical examination, medical history • Modified Rankin Scale • Spinal Cord Ischemia Scale • NIH Stroke Scale • Spiral Computed Tomographic Angiography (CTA) of the chest, abdomen, and pelvis (contrast only) within 90 days prior to enrollment • Serum creatinine concentration 
Procedure:
 
 • Endovascular repair with the TBE Device with distal extension using the Conformable GORE® TAG® Thoracic Endoprosthesis as needed • Post deployment angiogram

	
Post Procedure: (Performed prior to discharge unless otherwise noted)
 
 • Physical examination • Modified Rankin Scale • Spinal Cord Ischemia Scale • NIH Stroke Scale • In addition, NIH Stroke Scale should be performed for any Subject suspected of having a stroke event that undergoes the treating site's stroke Protocol during the study interval from the initiation of index endovascular procedure until discharge, and should be performed as soon as possible after learning of the event 
Follow-Up Evaluations: Intervals: 1, 6, 12, 24, 36, 48, and 60 months post-treatment
 
 • Physical examination • Modified Rankin Scale (also completed at 3 months for Subjects suspected of experiencing a stroke event through 30 days) • Spinal Cord Ischemia Scale • Spiral CTA of the chest (contrast) • NIH Stroke Scale (one month only) • Dissection Subjects only: Spiral CTA of the chest, abdomen, and pelvis (contrast) • Spiral CT of the chest (non-contrast - one month only, or if endoleak suspected) • Dissection Subjects only: Spiral CTA of the chest, abdomen, and pelvis (non-contrast - one month only, or if endoleak suspected)

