5.1.3 Additional Analyses

The analysis population for all other analyses (outlined in **Section 5.5**) for each of the cohorts will be among enrolled Subjects (excluding those with a CEC adjudicated 'major' inclusion/exclusion criteria violation or FDA mandated exclusion). Any additional analysis population details are outlined in the appropriate subsection of **Section 5.5**.

5.2 **Timing of Analyses**

Prior to primary analysis, the composite Primary Endpoint results

will not be analyzed (except as detailed below in Section 5.2.2) for the two hypothesis-driven test arms. Serial analyses of long-term results will occur during the follow-up period. A final analysis will be conducted once study follow-up is complete. In addition to the Primary Endpoint at primary analysis time points, all other additional analyses (detailed in Section 5.5) will also be performed.

Details on primary analysis timing are provided in the below subsequent sections:

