5.3 Primary Endpoint Analysis

5.3.1 Zone 2 and Zone 0/1 Aneurysm Cohorts

The proportion of composite Primary Endpoint success (1 - composite Primary Endpoint failure) will be calculated for each hypothesis-driven cohort based on the details outlined for each Primary Endpoint component in **Appendix A**. One-sided Exact confidence intervals for binomial proportions (alpha=0.05) will be constructed to test each calculated composite proportion against the respective Primary Endpoint hypothesis. Each hypothesis-driven cohort tested must meet their respective Primary Endpoint analysis population criteria. The null hypothesis will be rejected if the lower bound of the 95% confidence interval estimating composite Primary Endpoint success exceeds the performance goal.

In addition, the Primary Endpoint data (composite and components) for each of these two cohorts will be summarized by statistics (count and percent).

In order to assess the impact of missing data on each of the composite Primary Endpoint hypothesis tests, sensitivity analyses will be performed and are outlined in **Section 5.5.1**.

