5.5.7 Reinterventions

A Site-reported reintervention will be counted as occurring if the Site reports a 'yes' to the question "Was reintervention on the treated segment of the branch vessel or the aorta performed?" from the AE CRF. The incidence of Site-reported reinterventions will be summarized by analysis time window among those remaining in follow-up. In addition, the time to first Site-reported reintervention will be calculated using Kaplan Meier methodology. Subjects without a Site-reported reintervention reported before the end of the time period of interest will be censored at the Subject's last reported contact date or the end of the time period of interest, whichever date is earlier.

Unanticipated additional procedures related to the device, procedure, or withdrawal of the delivery system (meeting Primary Endpoint or Success Outcome criteria) will be summarized in the Primary Endpoint and Success Outcome tables and are not reconciled with Site-reported reinterventions as described above.

Initially treated Zone 2 cohort Subjects that have a reported reintervention involving Zone 0/1 treatment will remain in their original enrolled cohort for statistical analysis but narratives will be provided on these Subjects in submissions to the FDA (in all appropriate sections of the submitted report). In addition, the number and percent of these Subjects will be summarized.

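### Kaplan-Meier for first reintervention (SAP 5.5.7) censors deaths by implication, so 1-KM overstates the share of subjects reintervened at late follow-up; report cumulative incidence (minor)

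*SAP*

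**What the plan says.** **Reintervention (SAP 5.5.7).** The SAP states that "the time to first Site-reported reintervention will be calculated using Kaplan Meier methodology". On censoring it states: "Subjects without a Site-reported reintervention reported before the end of the time period of interest will be censored". The censoring date is the earlier of last reported contact and the end of the period. A second summary is planned: "The incidence of Site-reported reinterventions will be summarized by analysis time window among those remaining in follow-up".

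**Lesion-related mortality (SAP 5.5.6).** "For additional analysis of lesion-related mortality (in addition to Primary Endpoint and Success Outcomes), Kaplan Meier methodology will be used". The censoring rule has the same form: "Subjects without a lesion-related death reported before the end of the time period of interest will be censored".

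**All-cause mortality (SAP 5.5.6)** is also estimated by Kaplan-Meier.

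**Horizon.** SAP 5.2 states: "Serial analyses of long-term results will occur during the follow-up period". The follow-up schedule in the Protocol Summary runs to five years: "Intervals: 1, 6, 12, 24, 36, 48, and 60 months post-treatment".

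Neither section says how to treat a subject who dies before a reintervention, or who dies of a cause unrelated to the lesion. The public text contains no cumulative incidence function, no competing-risk method and no statement of which risk the curves are meant to estimate.

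**The concern.** A subject who has died without a reintervention is a subject without a reintervention. Under the rule in 5.5.7 the only place for that subject is among the censored. Kaplan-Meier treats a censored subject as still able to have the event later, with the same hazard as those under observation. A dead subject cannot. On the same data, 1-KM is therefore at or above the Aalen-Johansen cumulative incidence, and strictly above it once events follow competing deaths.

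What is at stake is a descriptive figure: the proportion of treated subjects who need a reintervention by a late time point. A reader of a five-year report is likely to take 1-KM as that proportion. No other output in the public text gives it. The by-window incidence conditions on subjects still under follow-up at that window, so it is not cumulative.

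**Working it through.** The SAP states no figure for these curves, so there is none to reproduce. The check has two parts: what the planned outputs can deliver, and how large the gap might be.

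**1. Can the cumulative incidence be recovered from planned outputs?**

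- The cumulative incidence adds up, over event times, (probability of being free of the event and alive just before t) × (event hazard at t).
- *Lesion-related mortality: yes.* The first factor is all-cause survival, which 5.5.6 plans. The second comes from the steps of the lesion-related curve, also planned. In addition, 5.3.1 gives counts and percents of the primary endpoint components (through day 546 in Zone 2 and day 59 in Zone 0/1). Sections 5.1.1.2 and 5.2.2 repeat the Zone 0/1 analysis with 12-month results. The wording of 5.5.6 indicates that lesion-related mortality is also a Success Outcome.
- *First reintervention: no.* The first factor is reintervention-free survival, which the public text does not plan. Multiplying the reintervention and all-cause curves would give it only if death were unrelated to reintervention.

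**2. Size under assumed rates**

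Inputs, all assumed: at T = 60 months, 1-KM for the event is 20% and competing death is 30%, also on the 1-KM scale. The death hazard is constant.

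- H1 = -ln(0.80) = 0.2231 and H2 = -ln(0.70) = 0.3567.
- *Constant event hazard:* CIF = H1/(H1+H2) × (1 - exp(-(H1+H2))) = 0.2231/0.5798 × (1 - 0.80 × 0.70) = 0.3849 × 0.44 = 16.93%. Excess: 20 - 16.93 = 3.07 points.
- *80% of H1 in month 1, the rest even over months 1 to 60:*
  - Month 1: event 0.1785, death 0.0059, contribution 0.1630, event-free survival 0.8316.
  - Months 1 to 60: event 0.0446, death 0.3507, contribution 0.8316 × 0.1129 × 0.3266 = 0.0307.
  - CIF = 19.37%. Excess: 0.63 points.
- *50% of H1 in month 1:* the same steps give 0.1053 + 0.0794 = 18.47%. Excess: 1.53 points.

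A simulation of 2,000,000 subjects gave 16.95% (constant) and 19.36% (80% in month 1), which agrees.

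Excess of 1-KM in points, by time, for 20%/30%:

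| Event timing | 12 mo | 24 mo | 36 mo | 48 mo | 60 mo |
|---|---|---|---|---|---|
| Constant | 0.15 | 0.57 | 1.22 | 2.07 | 3.07 |
| 50% in month 1 | 0.10 | 0.30 | 0.61 | 1.03 | 1.53 |
| 80% in month 1 | 0.07 | 0.15 | 0.27 | 0.43 | 0.63 |

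These are scenarios, not bounds. If the event hazard instead rises linearly from zero, the excess at 20%/30% is 4.09 points. With 25% events, 50% competing death and constant hazards it is 6.67 points.

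For a rarer event such as lesion-related death, at 5%/30%, the 60-month excess is 0.79 points (constant), 0.40 (50% in month 1) or 0.17 (80% in month 1). At 12 months it is 0.02 to 0.04 points.

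**3. Scale against sampling error**

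The simple binomial standard error of 20% is sqrt(0.2 × 0.8/85) = 4.3 points at n=85 (Zone 2 Primary Enrollment) and sqrt(0.2 × 0.8/50) = 5.7 points at n=50 (Zone 0/1). At 20%/30% each computed excess is below one standard error. Unlike sampling error, it always has the same sign.

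**The case against.** **Kaplan-Meier with deaths censored is a coherent quantity.** It estimates a net (cause-specific) risk if censoring is independent, and the SAP never says the curve is the share of treated subjects with the event. This stands. A reader might infer that the analysis is simply wrong, but the documents do not support that. The gap is an unstated target, and the figure misleads only under one natural reading.

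**Part of the SAP is not public.** The text of 2.3.2, 5.1.2 and 5.4 and the output lists of Section 8 are missing, and a competing-risk or reintervention-free survival output could be there. This stands too. The point is limited to what the public text plans.

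**Lesion-related mortality is already covered.** A reader might infer that such deaths are counted only within the primary endpoint window. The documents do not support that, given the Zone 0/1 12-month repeat and the reference to Success Outcomes. The gap is also small if these deaths are few or early, and the cumulative incidence can be rebuilt. The live issue is 5.5.7.

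**Nothing is decided on these curves.** A reader might infer that the hypothesis tests are affected. They are not: 5.3.1 uses exact binomial intervals, and these are additional descriptive analyses. The bias also makes the device look worse, not better. All of this keeps the severity low. It does not remove the point, because late reintervention has no cumulative absolute-risk output in the public text.

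**Conclusion.** The point holds as a minor one, mainly for late reintervention. By implication 5.5.7 censors deaths before reintervention, so 1-KM is too high if read as the share of treated subjects reintervened. The direction is a mathematical property and needs no assumed rates.

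The size rests wholly on assumptions: about 0.6 to 3.1 points at 60 months for 20% reintervention and 30% death with constant or front-loaded reintervention, more if reinterventions come late, and negligible at 12 months. The same rule touches lesion-related mortality in 5.5.6, but less. All-cause mortality by Kaplan-Meier has no competing event and is sound.

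**What to change.** - In SAP 5.5.7, report the Aalen-Johansen cumulative incidence of first Site-reported reintervention with its confidence interval, naming death from any cause as the competing event.
- In SAP 5.5.6, do the same for lesion-related mortality, with non-lesion death as the competing event.
- If Kaplan-Meier is kept for these two outcomes, label it as a net-risk (cause-specific) summary.
- Keep Kaplan-Meier for all-cause mortality.
- If a non-public section already plans such an output, a cross-reference in 5.5.6 and 5.5.7 is enough.

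The cost is a few sentences and one extra standard output, with some departure from the familiar Kaplan-Meier display. No new data are needed: deaths, reinterventions and the adjudication of lesion-related mortality are already collected.

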5.5.7 Reinterventions

A Site-reported reintervention will be counted as occurring if the Site reports a 'yes' to the question "Was reintervention on the treated segment of the branch vessel or the aorta performed?" from the AE CRF. The incidence of Site-reported reinterventions will be summarized by analysis time window among those remaining in follow-up. In addition, the time to first Site-reported reintervention will be calculated using Kaplan Meier methodology. Subjects without a Site-reported reintervention reported before the end of the time period of interest will be censored at the Subject's last reported contact date or the end of the time period of interest, whichever date is earlier.

Unanticipated additional procedures related to the device, procedure, or withdrawal of the delivery system (meeting Primary Endpoint or Success Outcome criteria) will be summarized in the Primary Endpoint and Success Outcome tables and are not reconciled with Site-reported reinterventions as described above.

Initially treated Zone 2 cohort Subjects that have a reported reintervention involving Zone 0/1 treatment will remain in their original enrolled cohort for statistical analysis but narratives will be provided on these Subjects in submissions to the FDA (in all appropriate sections of the submitted report). In addition, the number and percent of these Subjects will be summarized.

5.5.8 Stroke and Paraparesis/Paraplegia

For additional analysis of these events (in addition to Primary Endpoint and Success Outcomes), all Subjects remaining in follow-up will be part of this analysis population. Event rates of each type of event will be displayed separately as well as an overall rate.

6.0 Interim Analyses and Safety Monitoring Analyses

There are no planned interim analyses of composite Primary Endpoint results for the two hypothesis-driven test arms.

However, safety data will be periodically reviewed by the DSMB (see **Section 4.4**). A comprehensive summary of reported adverse events will be reviewed by the DSMB on a regular and ongoing basis throughout the duration of the study. Safety data may be presented in various ways, such as serious adverse events vs. non-serious adverse events. In addition, adverse events resulting in mortality and/or in site-reported reinterventions may be presented separately.

Serial analyses of long-term results will occur during the follow up period.

GORE CONFIDENTIAL INFORMATION

7.0 Analysis Specifications

7.3 Verification Level for Statistical Output

All statistical output will be programmed per the Clinical Affairs Biostatistics Analysis SOP (MD111325)³.

The verification level scheme for regulatory submissions is provided below:

- All Analysis Datasets Level I
- All Tables Level I
- All Listings Level II

[figure not shown]
8.0 Data Sets, Tables, Figures, and Listings

This section includes a minimal list of planned statistical outputs for primary analysis, including tables, listings and figures. All output will be prepared by both study arms and cohort.

8.1 Analysis Tables

Appendix A: Adjudication of Primary Endpoints and Success Outcomes

[figure not shown]
The table below describes the responsible party for the determination and adjudication of each specific Primary Endpoint and The time periods for these endpoint/outcome determinations are described in Section 2.3. In addition, the third column explains what CRF, question (using permanent internal database short label), and question response will be used to determine endpoint/outcome failure.

[figure not shown]
Key Outcome	Endpoint/Outcome Determination	Case Report Form, Question Short Label (Response Option Picked to Determine Endpoint / Outcome Failure)
Device Technical Success for index endovascular procedure	Composite Event - Not Applicable	
Successful access and delivery	Site Investigator	TX2, Question 'TX2 Access' (No)
Patency of the graft	Site Investigator	 TX2, Question 'TX2 Patent' (No)
Unanticipated additional procedure related to the device, procedure, or withdrawal of the delivery system	Site Investigator	 TX2, Question 'TX2 Unanticipated' (Yes)
Aortic Rupture	Site Reported AE followed by CEC Adjudication Or Core Lab	 Event reported in AE form and CEC Adjudicated Question 'CEC Aortic Rupture' (Yes) or POSTCL-ANU, Question 'Post Lesion Rupture' (Yes – Within area of treatment) or POSTCL-DIS, Question 'Post Dis Rupture' (Yes – Within area of treatment) or Event reported in AE form and OMA Question 'OMA1 Aortic Rupture' (Yes)
Lesion-related Mortality	Site Reported AE followed by CEC Adjudication	 Death reported (AE, Question 'AE Outcome' (Death)) and CEC Adjudicated Question 'CEC Lesion Related Mortality 2' (Yes) or Death reported (AE, Question 'AE Outcome' (Death)) and OMA Question 'OMA1 Lesion Related Mortality 2' (Yes)
Disabling Stroke	Site Reported AE followed by CEC	Event reported in AE form and CEC8 or CEC9

GORE CONFIDENTIAL INFORMATION

Key Outcome	Endpoint/Outcome Determination	Case Report Form, Question Short Label (Response Option Picked to Determine Endpoint / Outcome Failure)
	Neurologist Review and adjudication	Question 'CEC Disabling' (Yes)
Permanent Paraplegia	Site Reported AE followed by CEC Adjudication	Event reported in AE form and CEC Adjudicated Question 'CEC Paraplegia' (Yes)
Permanent Paraparesis	Site Reported AE followed by CEC Adjudication	 Event reported in AE form and CEC Adjudicated Question 'CEC Paraparesis' (Yes)
Additional unanticipated post- procedural surgical or interventional procedure related to the device, procedure, or withdrawal of the delivery system	Site Reported AE with an unanticipated post- procedural surgical or interventional procedure followed by AE adjudication by CEC.	 Event reported in AE form where Site answers Question 'AE SAE Unanticipated' (Yes) and CEC Adjudicated Question 'CEC Reintervention' (Yes) or Event reported in AE form where Site answers Question 'AE SAE Unanticipated' (Yes) and OMA Question 'OMA1 Reintervention' (Yes)
Initiation of the index endovascular procedure following the debranching procedure (Zone 0/1 cohorts only)	Site Reported Treatment Data	PFU, Question 'PFU Continue' (No)

Key Outcome	Endpoint/Outcome Determination	Case Report Form, Question Short Label (Response Option Picked to Determine Endpoint / Outcome Failure)
